### 5.5. Compensation for Participation

Participants will be compensated up to \$325 for their time and effort as follows:

Initial Screening:	\$40	Day 11 Online Visit:	\$5
Medical Screening:	\$40	Day 12 Online Visit:	\$5
Cue-Exposure #1:	\$20	Day 13 Online Visit:	\$5
Day 1 In-person Visit:	\$30	Day 14 In-person Visit:	\$30
Day 8 In-person Visit:	\$50	Sleep Tracking Wristband:	\$20
Day 9 Online Visit:	\$5	Cue-Exposure #2:	\$20
Day 10 Online Visit:	\$5	Completion Bonus:	\$50

In addition, participants will have the opportunity to earn between 1¢ and \$30 in the form of cash or electronic gift card one week after the behavioral economics paradigm described above. All participants will be provided with free parking validation, round-trip bus fare or transportation via Uber for attendance to each study visit. Participants are free to discontinue participation at any time and will receive compensation for the amount of time they participated. The completion bonus will be given to participants who complete at least 7 of the 8 in-person and online study visits.

## 6. ASSESSMENTS

### 6.1. Schedule of Assessments Table

STUDY VISIT:	Initial Screening	Medical Screening	CR Sessions (Days 1 & 14)	Randomization (Day 1)	Practice Quit (Days 8-14)
SCREENING/INDIVIDUAL DIFFERENCE MEASURES:					
Alcohol Dependency Scale (ADS)				x	
Beck Anxiety Inventory (BAI)				x	x*
Beck Depression Inventory (BDI)				x	x*
Brief AUD Severity Scale				x	
Cannabis Use Disorder Identification Test (CUDIT)				x	
Demographics	x				
Fagerstrom Test for Nicotine Dependence (FTND)	x				
Family Tree Questionnaire (FTQ)				x	
Graded Chronic Pain Scale				x	
ImBIBe				x	
Inventory of Drinking Situations (IDS)				x	
Locator Form	x				
Monetary Choice Questionnaire (MCQ)				x	x*
Obsessive Compulsive Drinking Scale (OCDS)				x	x*
Penn Alcohol Craving Scale (PACS)				x	x*
Perceived Stress Scale (PSS)				x	
Pittsburgh Sleep Quality Index (PSQI)				x	x*
Readiness to Change (RTC) Ladder				x	
Self-Report Habit Index (SRHI) Drinking & Smoking				x	
Structured Clinical Interview for DSM-5 Screener & AUD Module	x				
Timeline Follow Back (TLFB)	x	x		x	x
UCLA Reward Relief Habit Drinking Scale (UCLA RRHDS)				x	
UPPS-P Impulsive Behavior Scale				x	
SAFETY MEASURES/BIOMARKERS:					
Adverse Events/SAFTEE					x
Alcohol Breathalyzer	x	x	x	x	x
Birth Control Assessment	x				
Clinical Institute Withdrawal Assessment (CIWA-AR)	x	x		x	x
Columbia Suicide Severity Rating Scale (C-SSRS)	x				
Comprehensive Metabolic Panel/Complete Blood Count		x			
Concomitant Medications	x	x		x	x
Electrocardiogram (EKG)		x			
Medical History/Physical Exam		x			
Urine Ethyl Glucuronide (EtG) Test					x
Urine Drug Screen	x	x		x	
Urine Pregnancy Test	x	x		x	x*
Vital Signs	x	x		x	x
EXPERIMENTAL MEASURES:					
Alcohol Purchase Task (APT)					x*
Alcohol Urge Questionnaire (AUQ)			x		
Daily Diary Assessment					x
Multiple Choice Procedure (MCP)					x*
Profile of Mood States (POMS)			x		

Sleep Tracking Wristband						x
*Measure collected on Day 14 only						

## **6.2. Description of Assessments**

### **6.2.1. Alcohol Dependency Scale**

The Alcohol Dependency Scale is a 25-item scale that measures alcohol dependence symptoms over the past 12 months. The ADS is a self-report measure that assesses problems that are relevant for alcohol dependent drinkers and will be completed by the participant electronically at the randomization visit.

### **6.2.2. Beck Anxiety Inventory (BAI)**

The Beck Anxiety Inventory (BAI) surveys anxiety symptomatology including physical and cognitive indicators of anxious mood. The BAI will be completed electronically at the randomization and final (Day 14) visit.

### **6.2.3. Beck Depression Inventory (BDI-II)**

The Beck Depression Inventory, Revised (BDI-II) captures depressive symptomatology. The BDI-II will be completed at the Day 1 (randomization), and Day 14 visits.

### **6.2.4. Brief AUD Severity Scale (BASS)**

The Brief AUD Severity Scale (BASS) is a 9-item self-report measure used to assess alcohol use disorder severity. The BASS will be completed at the randomization visit.

### **6.2.5. Cannabis Use Disorder Identification Test (CUDIT)**

The Cannabis Use Disorder Identification Test (CUDIT) is an 8-item measure used to screen for cannabis use disorders (CUD) and will be completed at the randomization visit.

### **6.2.6. Demographics**

Demographics data include the participant's age, gender, race/ethnicity, marital status, education, employment pattern, occupation, and income level. This questionnaire will be administered electronically at the initial screening visit.

### **6.2.7. Fagerström Test for Nicotine Dependence (FTND)**

The Fagerström Test for Nicotine Dependence will be used to assess smoking status at the initial screening visit. This questionnaire will be completed by the subject electronically.

### **6.2.8. Family Tree Questionnaire (FTQ)**

Information on family history of alcohol problems will be collected using the Family

Tree Questionnaire. The questionnaire provides subjects with a family tree listing of relatives to identify blood relatives with alcohol problems. This questionnaire will be completed by the subject electronically at the randomization visit (Day 1).

#### **6.2.9. Graded Chronic Pain Scale**

The Graded Chronic Pain scale is a 7-item measure used to evaluate an individual's overall severity of chronic pain if they have suffered from chronic pain that has lasted at least six months. The measure assesses on two dimensions: pain severity, and pain-related disability. This questionnaire will be completed by participants electronically at the randomization visit.

#### **6.2.10. ImBIBe**

The ImBIBe is a 15-item questionnaire in which the subject responds on a 5-point scale responses to questions on the consequences of alcohol use. The ImBIBe will be completed at the randomization visit (Day 1).

#### **6.2.11. Inventory of Drinking Situations (IDS)**

The Inventory of Drinking situations (IDS) is a questionnaire developed to characterize the particular high-risk situations of a problem drinker. The IDS will be completed by the participant electronically at the randomization visit.

#### **6.2.12. Locator Form**

The Locator Form asks participant to provide his/her name, address, and phone number and to provide names, addresses, and phone numbers of friends and family members who can be contacted if the subject cannot be located. This information is essential and will be collected during the initial screening, and will be updated throughout the study as necessary.

#### **6.2.13. Monetary Choice Questionnaire (MCQ)**

The Monetary Choice Questionnaire is a 27-item self-administered questionnaire in which the participant chooses between a smaller, immediate monetary reward and a larger, delayed monetary reward. The MCQ will be completed at randomization and Day 14 visit, as part of the behavioral economics paradigm.

#### **6.2.14. Obsessive Compulsive Drinking Scale (OCDS)**

The 14-item Obsessive Compulsive Drinking Scale (OCDS) is a quick and reliable self-rating instrument that provides a total and two subscale scores that measure some cognitive aspects of alcohol craving. The OCDS will be completed at the randomization and Day 14 visits.

#### **1.1.1. Penn Alcohol Craving Scale (PACS)**

The PACS is a five-item, self-report measure that includes questions about the frequency, intensity, and duration of craving, the ability to resist drinking, and asks for an overall rating of craving for alcohol for the previous week. Each question is scaled from 0 to 6. Participants will complete this scale at randomization and Day 14.

### **1.1.2. Perceived Stress Scale (PSS)**

The PSS is a measure of the degree to which situations in one's life are appraised as stressful. Items were designed to tap how unpredictable, uncontrollable, and overloaded respondents find their lives. The PSS will be completed at randomization.

### **1.1.3. Pittsburgh Sleep Quality Index (PSQI)**

The Pittsburgh Sleep Quality Index (PSQI) is a self-report questionnaire that assesses sleep quality over a 1-month time interval. The measure consists of 19 individual items, creating 7 components that produce one global score, and takes 5-10 minutes to complete. The PSQI will be completed at the randomization and Day 14 visits.

### **1.1. Readiness to Change (RTC) Ladder**

The Readiness to Change Ladder is a measure with 11 response items designed to assess motivation to reduce or cut back on drinking. This assessment will be completed at the randomization visit.

### **1.1.1. Self-Report Habit Index Form (SRHI)**

The Self-Report Habit Index (SRHI) is an instrument that measures self-reported perceptions of habit strength for an identified behavior. In addition to measuring prior behavior and automaticity, the SRHI measures identity expression as a component of habit. The SRHI will be assessed for drinking and smoking and will be completed at the randomization visit.

### **1.1.4. Sleep Tracking Wristband**

The Fitbit Charge 5 is a health tracker used as a passive sleep tracking device. Interested participants will be asked to wear the sleep tracking wristband every night during the practice quit attempt (Days 8 – 14). Sleep data from the previous day will be synced to the Fitbit app every day.

### **1.1.5. Structured Clinical Interview for DSM-5 Disorders**

The SCID is a semi-structured interview for making the major DSM-5 diagnoses. The SCID screener assessment and alcohol module, used to assess current (past 12-month) AUD diagnosis will be completed by appropriately trained research personnel. Any positive responses on the SCID screener will be further assessed by the study physician to determine eligibility.

### **1.1.6. Timeline Follow Back (TLFB)**

The Time Line Follow Back will be administered to assess quantity and frequency of alcohol, cigarette and marijuana use and will be completed at the initial screening (for the 30 days prior to that visit) and at each subsequent visit, including phone visits, to gather data for every day prior to and including the last visit. Information obtained in this interview will be recorded on the TLFB Calendar and transcribed to the database.

#### **1.1.7. UCLA Reward Relief Habit Drinking Scale (UCLA RRHDS)**

The UCLA RRHDS is a 4-item self-report questionnaire to assess reward, relief and habit drinking sub-types. It will be completed electronically at the randomization visit.

#### **1.1.8. UPPS-P Impulsive Behavior Scale**

The UPPS-P Impulsive Behavior Scale is a 59-item self-report that assesses five subscales (urgency, premeditation, perseverance, sensation seeking, and positive urgency) that are used to measure 5 distinct dimensions of impulsive behavior. This measure will be completed electronically at the randomization visit.

#### **1.1.9. Adverse Events/SAFTEE Assessment**

On each day of the practice-quit attempt (Days 8-14) participants will be asked by study staff if they have experienced any symptoms or side effects since the last visit. With guidance from the study physician, each participant response will be coded into one of the listed items on the SAFTEE (Systematic Assessment of Treatment Emergent Effects).

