### 5.4. Medication Phase

#### 5.4.1. Randomization and Medication Titration

Participants who are eligible after the physical exam will be randomized to one of three treatment conditions (VAR, NTX, or PLA). Urn randomization will be used to balance the groups by gender, smoking status (as reported on question 1 of the Fagerstrom Test for Nicotine Dependence), and drinking status ('heavy' drinker defined as 14 or more drinks per week for

males/7 or more drinks per week for females, or 'very heavy' drinker, defined as 35 or more drinks per week for males/28 or more drinks per week for females). The UCLA Research Pharmacy will manage the blind. The three treatment conditions will not be different in appearance or method of administration. All participants will undergo a week-long medication titration period prior to the onset of the practice quit attempt.

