#### 5.4.3. Study Medication

On Day 1, participants will report to the laboratory to complete the alcohol cue-reactivity paradigm and receive their first medication dose under direct observation of study staff. They will receive a 7-day supply of study medication in blister packs with AM and PM dosing clearly distinguished for the titration procedure. After reaching full medication dose at the end of one week, participants will come to the laboratory on Day 8 to receive their second, 7-day supply of study medication and to begin the 7-day practice quit attempt. Participants will be asked to take AM dose of study medication on Day 8 in the lab under direct observation of study staff. All study medication will be prepared by the UCLA Research Pharmacy and will be identically matched in appearance (opaque capsules) and the medication labels will not reveal the drug identity.

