#### **2.1. PI and Study Physician Safety Monitoring**

Participants will be given a 24-hour telephone number for calling the physician to discuss side effects, and physician office hours will be available as needed. Adverse events, including signs of sickness will be collected in an open-ended way at each in-person and phone study visit. Vital signs will be monitored at multiple time points during the experimental study visits. Alcohol withdrawal will be monitored at each visit through administration of the CIWA, and any significant withdrawal, as indicated by a score of 10+ on the CIWA will be reported to the study physician immediately. In the event that significant medical problems are encountered, the study blind will be broken and appropriate medical treatment will be provided.

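### Adverse-event questions are scheduled from Day 8 although dosing starts on Day 1 and the safety plan says every visit: no pre-dose SAFTEE record, and titration-week leavers are not actively asked

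*Combined protocol and SAP*

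**What the plan says.** Three places set the timing of the question.

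- **Adverse Events/SAFTEE Assessment:** "On each day of the practice-quit attempt (Days 8-14) participants will be asked by study staff". The question reaches back to the previous contact, and each answer is coded to a SAFTEE item with guidance from the study physician.
- **6.1 Schedule of Assessments Table:** the row "Adverse Events/SAFTEE" carries one mark, which reads as the practice-quit column. Screening and Day 1 are unmarked.
- **PI and Study Physician Safety Monitoring:** adverse events "will be collected in an open-ended way at each in-person and phone study visit".

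Section 5.4.2 also has staff ask about adverse events in the daily calls, which fall inside the quit period.

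On dosing, section 5.4.3 has participants attend on Day 1 and "receive their first medication dose under direct observation of study staff". Section 5.4.1 adds: "All participants will undergo a week-long medication titration period prior to the onset of the practice quit attempt". The next visit is a week later, when "participants will come to the laboratory on Day 8 to receive their second, 7-day supply of study medication".

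The safety monitoring section also gives participants a physician's telephone number that is staffed round the clock. No early-termination visit, and no call to people who stop attending, is described.

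**The concern.** The first dose comes a week before the first scheduled adverse-event question, and that week is the dose-escalation week. Two things could be lost.

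The first is a reference point. SAFTEE is meant to capture treatment-emergent effects. Without the same items recorded before dosing, and with no rule that an event must be new or worse, a complaint that was already there can be counted as emerging on treatment.

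The second is the experience of people who stop during escalation. Some may stop because of side effects, and theirs are the events a tolerability summary most needs. Section 2.2 names safety and tolerability as one of the two endpoints that human laboratory methods address, so the gap bears on a stated purpose of this kind of study.

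**Working it through.** **1. Visit count.** Section 5.5 ties the completion bonus to 7 of 8 in-person and online visits. Its payment list gives Day 1, Day 8, Days 9-13 online and Day 14: 1 + 1 + 5 + 1 = 8. The stated figure is reproduced, and only if Day 1 counts as a study visit. No visit falls on Days 2-7.

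**2. Visits that carry the question.**

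| Source | Day 1 | Days 2-7 | Days 8-14 |
|---|---|---|---|
| SAFTEE section and 6.1 | no | no visit | yes (7 visits) |
| Safety monitoring section | yes | no visit | yes (7 visits) |

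The schedule covers 7 of the 8 visits and the safety plan covers all 8 (read literally, the screening visits too). The sources differ at Day 1. The table's layout may have suffered in extraction, but the prose of the SAFTEE section states the same limit.

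**3. Dosing before the first scheduled question.** Dosing runs over Days 1-14. Days 1-7 are complete before the Day 8 visit, so 7 of the 14 dosing days precede it.

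**4. Who is asked about the titration week.**

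- A participant who attends Day 8 is asked about the time since the previous visit, which was Day 1. The titration week is covered retrospectively.
- A participant who leaves on Days 1-7 is never asked under the schedule.
- Under the safety plan that participant could be asked on Day 1, but not about any later day, because no contact follows.

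**5. What is on record before dosing.** Medical screening (5.3.3) takes medical history, physical examination, review of systems, vital signs, laboratory tests and EKG. CIWA-Ar is taken at screening and on Day 1. BAI, BDI and PSQI are completed at the randomization visit. SAFTEE items are not scheduled at any of these points. If the safety plan governs, a Day 1 question exists, but no text places it before the dose or codes it to SAFTEE.

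**6. Possible number affected.** Statistical Power plans 108 randomized (36 per group) and 90 completers (30 per group).

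- Planned non-completers: 108 - 90 = 18, or 36 - 30 = 6 per group.
- Share of those randomized: 18/108 = 16.7%.
- With a share s of the 18 leaving on Days 1-7, the number never asked under the schedule is 18 × s. The documents do not give s, so the full range is shown.

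| s (assumed) | Never asked | Share of 108 |
|---|---|---|
| 0% | 0 | 0% |
| 50% | 9 | 8.3% |
| 100% | 18 | 16.7% |

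**The case against.** The other side has a good deal to say.

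- **The contradiction is narrow.** The versions differ in practice at Day 1, when almost no time on drug has passed, and the Day 8 question reaches back over titration. This stands for everyone who attends Day 8. A reader might infer that the titration week goes unobserved for the whole sample; the recall wording does not support that.
- **There is pre-dose information.** A reader might infer that all 108 enter with no baseline. The screening and randomization measures show otherwise. What is missing is a record in SAFTEE format, and the physician guiding the coding can consult the screening history. Miscoding is therefore possible, not certain.
- **A Day 1 record would not isolate withdrawal symptoms.** It is tempting to say that a baseline would separate symptoms of stopping alcohol from drug effects. The instruction to abstain starts on Day 8 (5.4.2), after any Day 1 record. The placebo arm and CIWA-Ar at each medication-phase visit address that question.
- **A reporting route exists.** The telephone line is open throughout. It depends on the participant ringing, so it does not replace a question put to everyone.
- **No planned comparison is biased.** A reader might conclude that the active arms will be shown as safer than they are. The Data Analytic Plan specifies no between-arm safety analysis, and the missing baseline is common to all three arms. Selective early loss could still distort a descriptive tolerability summary.

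None of this removes the conflict between the sections or supplies an active question to people who leave before Day 8.

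**Conclusion.** The point holds as a minor one. The SAFTEE section and the schedule contradict the safety monitoring section on Day 1. Followed as scheduled, the plan has no pre-dose SAFTEE record and puts no adverse-event question to titration-week leavers. Adopting the safety plan's wording repairs this only in part, because Days 2-7 still hold no contact.

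The size can be bounded but not estimated. The bound in the working assumes that attrition matches the plan's allowance, and a figure inside it would need drop-out timing that the documents do not give. The effect is on completeness and coding of safety data; the drinking and craving analyses are untouched.

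**What to change.** 1. Reconcile the SAFTEE section, the schedule in 6.1 and the safety monitoring section so that they name the same visits.
2. Mark adverse events for Day 1 in 6.1, and record the SAFTEE items at that visit before the first dose.
3. State that an event counts as treatment-emergent only if it is new or worse than that record.
4. Add one telephone call, using the Locator Form details, to anyone who does not attend Day 8, and ask the same adverse-event question. This is a new procedure and should be written in as one.

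The cost is a table correction, a few minutes at an existing visit, and a small number of calls: no more than 18 if attrition is as planned and every non-completer leaves before Day 8. No visit is added. The call will not reach everyone, so the report should say how many early leavers were and were not asked.

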#### **1.1.10. Alcohol Breathalyzer**

An alcohol breathalyzer will be administered at consent, and at every in-person study visit as a safety measure. BrAC must be equal to 0.000 prior to performing any study assessments. Results will be recorded on the paper checklist, and later entered into the database.

#### **1.1.11. Birth Control Assessment**

The Birth Control Assessment is designed to confirm a female subject's compliance with the birth control specifications detailed in the inclusion criteria. Birth Control Assessment information will be recorded on the checklist at the initial screening visit for participant safety purposes.

#### **1.1.12. Clinical Institute Withdrawal Assessment for Alcohol (CIWA-Ar)**

The CIWA-AR is a brief 10-item measure used to provide a quantitative index of the severity of the alcohol withdrawal syndrome. The CIWA-AR has been used both in clinical and research applications and has demonstrated both reliability and validity. This questionnaire will be administered by appropriately trained staff during the initial and medical screening, and at each visit during the medication phase. Participant responses will then be entered electronically.

#### **1.1.13. Columbia Suicide Severity Rating Scale (C-SSRS)**

The C-SSRS is a 4-page form asking questions about suicidal ideation, intensity of ideation, and suicidal behavior developed by Posner and collaborators at the New York State Psychiatric Institute. This scale is intended for use by trained administrators. The questions contained in the C-SSRS are suggested probes. Ultimately, the determination of the presence of suicidality depends on clinical judgment. Training is required before administering the C-SSRS through a 30-minute interactive slide presentation followed by a question-answer session through the Columbia University Medical Center. Those completing the training are certified to administer the C-SSRS, and will receive a training certificate. This scale will be used to assess current

suicidal ideation at each visit and will be administered at the initial screening visit by a trained staff member with responses recorded on paper first, then entered electronically.

